#### **6.1.3 Handling, storage, accountability**

All the information collected though this study will go through [name]. All files will all be stored in the office. Everyone involved in this study will accept responsibility for

all the documents and results of this study.

#### **6.1.4 Required training**

All involved people have been properly trained to work with the patients and around the laser by [name].

#### **6.1.5 External studies**

In the event that plans are made to conduct additional studies, new protocols describing the relevant handling, storage, accountability, and training procedures will be prepared specifically for those studies.

### **6.2 Other Study Materials**

#### **6.2.1 Materials to be provided by study site**

- Study notebooks to maintain study documents, including signed ICFs, all applicable information, and additional forms to be collected and retained by the study institution during the course of the study.

#### **6.2.2 Materials to be provided by external testing facilities**

None

### **6.3 Consent Procedures**

This study will be held in the office of [name]. There will be no extra costs to participate in the study. The consent procedures will be read in office and there will be an opportunity to ask questions. Participation is voluntary. Once the consent form is read signed, and all questions are asked and the participant is aware of everything that will be done the consent form will be collected and he/she is ready to move forward with the study.

## 7 STUDY PROCEDURES

### 7.1 Workflow

This study will consist of two procedures. Both procedures will be performed on the same patient. Both procedures are cavity preparations. The tooth is chosen and the first procedure is started. The first one will be done with LLLT protocol prior to using the higher power to perform the cavity preparations. The second preparation will be done without LLLT first and thus using the higher power laser for cavity preparation from the beginning.

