## **LIST OF FIGURES**

**No table of figures entries found.**

## 1 INTRODUCTION

General dentistry can be stressful to both the patient and the doctor due to the fear of the needle before most dental procedures. One of the main benefits of using Lasers is pain reduction and anti-inflammation. In some of the references, scientists use electrodes inserted in the brain of cats or rabbits. They have also placed electrodes in the pulp of teeth to measure action potentials as pain is perceived or attenuated. They were able to show that pain causes action potential formed and pain reduction (analgesia) causes diminishing effects on the action potential. However, this is not practical in human study. Using the Visual Analog Scale (VAS) is a good way in gauging the patient's experience of the procedures. Small, medium, and large sized cavity preparations all to be measured. Effort is made to standardize the amount of cutting with each technique. The study is aimed to show if there is Laser Analgesia and if the use of Low Level Laser Therapy makes a difference in providing better analgesia.

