## 4 STUDY OVERVIEW

### 4.1 Study Approach

[figure not shown]
**Treatment.** Preconditioning and cavity preparation are done using the Er:Cr:YSGG laser, Waterlase MD (mfg: Biolase Technology Inc, Irvine CA), and the gold hand piece with an MG6 fiber tip, trunk fiber, contra-angle hand piece. *Preconditioning.* Preconditioning is preformed using laser desensitization. One tooth will be randomly selected, and preconditioning will be performed using LLLT on the tooth with minimal tooth ablation. The LLLT settings that will be used for preconditioning are 0.25 Watts, 50 Hz, 0% water, 0% air, H mode. Following this a fiber-optic tip will be aimed perpendicular to the surface of the cervical portion of the tooth, ensuring that a 2mm distance will be maintained between the end of the fiber optic tip and the surface. The fiber-tip will be used to generate a 2mm line. The cavity on the second tooth will be prepared for without laser preconditioning. *Lesion Preparation – small preparations.* Small preparations are to be performed as follows. The Waterlase MD is set to 4.5W, 15 Hz, 65% air, and 60% water and the cavity is prepared according to the preferred technique. If patients indicate sensitivity, the procedure will be halted, patients fill out the VAS form and anesthetic will be offered. For patients who refuse anesthetic, the procedure will be continued at the same settings. *Lesion Preparation – small to medium preparations.* Small to medium preparations will be performed as follows. The Waterlase MD will be set to 2W, 15 Hz, 65% air, and 60% water and the cavity will be prepared according to the preferred technique. If patients indicate sensitivity, the procedure will be halted, patients fill out the VAS form and anesthetic will be offered. For patients who refuse anesthetic, the procedure will be continued at the same settings.

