#### **Laser Preconditioning:**

- A. Laser Desensitization/ preconditioning procedure
  - a. Randomly select one tooth to have laser preconditioning performed on it
    - Preconditioning is using some LLLT on the tooth without expecting much, if any, ablation of the tooth.
    - For preconditioning, the setting is 0.25 Watt, 50Hz, 0% water, 0% air, H mode.
  - b. Aim fibre-optic tip perpendicular to the surface of cervical portion of tooth
  - c. Ensure that a 2mm distance between the end of the fiber optic tip and the surface is maintained
  - d. Go back and forth with the fibre-tip over a 2mm line for the number of seconds indicated
  - e. Prep the cavity on the first tooth (settings to follow)
  - f. Prep the cavity on the second tooth, without laser preconditioning

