## **9.2 Bias Minimization**

All subjects meeting the specified eligibility criteria will be enrolled in the study until all spots are filled up.

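### The LLLT tooth is always prepared first and the no-LLLT tooth second, so the LLLT comparison cannot be separated from an order effect

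*Protocol*

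**What the plan says.** Section 7.1 (Workflow) describes two cavity preparations in the same patient and ties each treatment to a position in time. For the LLLT preparation: "The first one will be done with LLLT protocol prior to using the higher power to perform the cavity preparations". For the other: "The second preparation will be done without LLLT first and thus using the higher power laser for cavity preparation from the beginning".

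The step list under Laser Preconditioning in section 7.1 gives the same sequence. Step a reads "Randomly select one tooth to have laser preconditioning performed on it". Steps b to d carry out the preconditioning, step e is "Prep the cavity on the first tooth (settings to follow)", and step f is "Prep the cavity on the second tooth, without laser preconditioning". Section 4.1 agrees: "One tooth will be randomly selected, and preconditioning will be performed using LLLT on the tooth with minimal tooth ablation", and it too calls the tooth without preconditioning the second one.

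Two sections could have held a safeguard. Section 7.3 (Randomization and Blinding) deals only with confidentiality. The text of section 9.2 (Bias Minimization) is one sentence: "All subjects meeting the specified eligibility criteria will be enrolled in the study until all spots are filled up".

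The comparison is a stated aim. The Introduction asks "if the use of Low Level Laser Therapy makes a difference in providing better analgesia", and sections 2.2 and 3 repeat the question.

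**The concern.** The random draw decides which tooth receives LLLT. It does not decide when: whichever tooth is drawn is prepared first. The draw therefore balances tooth characteristics between the two treatments and leaves treatment and position identical in every patient.

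The outcomes are a patient-marked VAS and the number of hand raises, and both could shift between a first and a second procedure. Fatigue or sensitisation would raise the second score and make LLLT look better than it is. Easing anxiety, or an analgesic effect carried over from the first tooth, would lower the second score and hide a real benefit. The protocol does not say whether both preparations fall in one visit, or how far apart they are, so neither the direction nor the size can be judged in advance. A positive or a null result on LLLT would be equally hard to interpret.

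**Working it through.** **Inputs from the protocol.** Two preparations per patient, LLLT first and no LLLT second (7.1); VAS from 0 to 100, lower is better (4.1); about 48 patients (9.1).

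**The planned number.** The formula in 9.1 with c = 1.96 throughout gives 1.96² × 50 × 0.25 / (0.025² × 50 + 1.96² × 0.25) = 48.02 / 0.99165 = 48.42, as stated. (The printed numerator has 1.69, which would give 36.00. That is a separate matter; 48 is used below.) This calculation contains no order effect, no SD and no LLLT contrast, so the protocol has no figure of its own on the present point.

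**Identifiability.** Let d be the no-LLLT score minus the LLLT score in one patient, β the true reduction from LLLT, and π the shift from first to second preparation.

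- Fixed order, all patients: E(d) = β + π. There is one equation for two unknowns. The design matrix with intercept, LLLT and second position has rank 2 of 3.
- Order balanced 24:24: E(d) = β + π when LLLT is first and β − π when it is second. Half the sum of the two group means is β; half the difference is π. The rank is 3 of 3.

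This result needs no numerical assumption.

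**Illustration of size (everything except the 48 is assumed).** Two-sided 5% one-sample t test on the paired differences, β = 0, normal differences. The noncentrality is π√n / SD; for example 5 × √48 / 15 = 2.31 and 5 × √48 / 30 = 1.15. Rejection rates, which should be 5%:

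| Pairs | Order shift | SD 15 mm | SD 20 mm | SD 25 mm | SD 30 mm |
|---|---|---|---|---|---|
| 48 | 2 mm | 14.8% | 10.4% | 8.4% | 7.4% |
| 48 | 5 mm | 61.9% | 39.6% | 27.4% | 20.5% |
| 24 | 5 mm | 34.7% | 21.7% | 15.6% | 12.3% |

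The 24-pair row is included because 6.1.2 may remove procedures finished under injection; its wording is ambiguous and 24 is only an assumed value.

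Section 4.1 scores zero for a patient who never raises a hand, so some patients may score zero on both teeth and show no shift. By simulation (40,000 runs per cell, SD 15 to 30 mm, 48 pairs), the 5 mm rate becomes 46.5% to 15.4% if 30% of patients are double zeros and 27.4% to 10.2% if 60% are. With 60% double zeros, a 2 mm shift gives 8.4% to 5.8%.

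The same arithmetic works the other way. If LLLT truly lowers the score by 10 mm and the second preparation is rated 5 mm lower because of order, the mean difference is 10 − 5 = 5 mm. The rejection rate is then the 61.9% to 20.5% of the table, against 99.5% to 62% without an order effect.

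**After balancing the order.** With 24:24 and position in the analysis, simulated false rejection is 4.5% to 5.1% for shifts of 2, 5 and 10 mm, at 0, 30 or 60% double zeros, with mean bias within 0.02 mm of zero. Power for a true 10 mm benefit with a 5 mm order shift is 99.5% (SD 15 mm) to 61.7% (SD 30 mm), the same as a paired test with no order effect.

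**Carry-over.** Suppose LLLT given first also lowers the second tooth's score by λ. The bias is π − λ in the fixed order and −λ/2 when balanced. For λ = 2, 5 and 10 mm the balanced bias is 1, 2.5 and 5 mm in size: half the carry-over component, whatever π is.

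**The case against.** The best defence of the text is the random choice of tooth in 4.1 and 7.1. If first and second were mere labels for the teeth, the order might be free. Section 7.1 does not allow that reading: it starts the first procedure and then assigns LLLT to it, and the step list has the same sequence. Randomising the tooth is worth keeping, but it does not vary order.

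A second argument concerns importance. Section 3 names proof of laser analgesia as the principal objective, the synopsis objective omits the LLLT contrast, and section 9.3 does not name it. This is fair as to hierarchy, and the finding does not touch that objective. But the Introduction and sections 2.2 and 3 all state the LLLT question, and it is the contrast for which each patient has two teeth treated.

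Third, the numerical illustration rests on assumed values and runs from about 6% to 62%. That stands: it shows that the problem can be negligible or severe, and the conclusion does not depend on it. Fatigue, sensitisation and carry-over also depend on how close together the two preparations are, which the protocol does not say. Familiarity or anxiety could still act across visits.

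Fourth, balancing is not a complete cure. With a 5 mm order shift against LLLT's comparator and carry-over of 2, 5 or 10 mm, the fixed-order bias is +3, 0 or −5 mm, so the two can cancel by chance. Nobody could know that they had. Expectation in an unblinded pain rating would also remain. These are limits of the remedy; they do not defend the fixed order.

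**Conclusion.** The point holds and must be fixed before enrolment. Under section 7.1 the LLLT effect and the order effect are completely confounded in every patient, and no later analysis can undo this because the reverse order never occurs. This conclusion rests on the protocol's text alone. The possible size is unknown: under the assumptions shown, a 5 mm order shift with 48 pairs turns a 5% error rate into 21% to 62%, or 10% to 27% if 60% of patients score zero on both teeth, and a 2 mm shift does much less. The finding is limited to LLLT against no LLLT and says nothing about the principal objective.

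**What to change.** In sections 4.1, 7.1 and 7.3, keep the random choice of tooth and add a second random draw per patient, 1:1 and in blocks, that decides whether the LLLT or the no-LLLT preparation is done first. Because this is one unblinded office, conceal the list and do not disclose the block sizes, so that the next order cannot be predicted. Replace the fixed first and second wording in 7.1, and have steps e and f refer to the randomised order. Compare the paired differences with position (period) in the analysis.

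Leave all laser settings as they are, keep preconditioning before the LLLT tooth's own preparation, and add no new timing interval.

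The cost is protocol wording and one extra draw per patient. The number of patients stays at 48, and in the simulations power is the same as for a paired test without an order effect. The remaining limit should be stated in the protocol: carry-over from a tooth treated first with LLLT is halved, not removed, so 5 mm of carry-over would still bias the contrast by 2.5 mm.

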#### **Laser Preconditioning:**

- A. Laser Desensitization/ preconditioning procedure
  - a. Randomly select one tooth to have laser preconditioning performed on it
    - Preconditioning is using some LLLT on the tooth without expecting much, if any, ablation of the tooth.
    - For preconditioning, the setting is 0.25 Watt, 50Hz, 0% water, 0% air, H mode.
  - b. Aim fibre-optic tip perpendicular to the surface of cervical portion of tooth
  - c. Ensure that a 2mm distance between the end of the fiber optic tip and the surface is maintained
  - d. Go back and forth with the fibre-tip over a 2mm line for the number of seconds indicated
  - e. Prep the cavity on the first tooth (settings to follow)
  - f. Prep the cavity on the second tooth, without laser preconditioning

#### **Preparation of Lesion:**

- A. Laser ablation- Small Preparation
  - a. Waterlase MD settings: 4.5W, 15Hz, 65% air, 60% water
  - b. Prepare cavity preparation using preferred technique
  - c. If the patient indicates sensitivity,
    - Halt the procedure
    - Have the patient mark the VAS form,
    - Offer anaesthetic; if refused, continue using the same settings
- B. Laser ablation- Small and Medium Preparation
  - a. Waterlase MD settings: 2W, 15Hz, 65% air, 60% water
  - b. Prepare cavity preparation using preferred technique
  - c. If the patient indicates sensitivity, either
    - Halt the procedure

- Have the patient mark the VAS form,
- Offer anaesthetic; if refused, continue using the same settings

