iplus offers complete versatility across all tissue types. It is engineered to provide a refreshing, comfortable patient experience when compared to traditional tools. It is cleared for over 80 different indication for soft tissue, hard tissue and bone. This is more than any other dental laser out there. Waterlaser iplus leads to results by empowering dentists to offer the best possible dental experience with single-visit, multi-quadrant, minimally invasive dentistry. This system is reliable, durable and flexible for any dental practice.

Er, Cr:YSGG laser system (2790nm, middle infrared) for cavity preparation and caries removal without the need of injection is one of the most attractive advantages of using the laser [4 , 5, 16, 17, 18, 19]. Due to the plentiful amount of water and air cooling in the Er:Cr:YSGG laser, there is no temperature change on the surface.[6] There is already the benefit of no side effect of heat on the surface of treatment. Different techniques are being used to achieve cavity preparation with the Er:Cr:YSGG laser system with no injection anesthesia [7]. The results claimed by using the different techniques are generally presented based on anecdotal evidence. One group of users may use one setting, typically at higher power levels, to perform the entire cavity preparation. A few of these high power examples are 6 Watts at 20 Hz, 4.5 Watts at 15 Hz, or 3 Watts at 10 Hz. Another group of users may use a moderate power setting to perform the entire cavity preparation such as 4.5 Watts at 20 Hz, 3.5 Watts at 15 Hz, or 2.5 Watts at 10 Hz and the setting is used. A third group of users use different settings for each step of the cavity preparation. They start out using relatively lower power such as 2 Watts, 30 Hz at a new lesion on the occlusal surface. The power is incrementally raised over time until ablation of the tooth takes place. After the cavity is removed, a lower power setting is used to finish and smooth the final preparation. The setting used is 2 Watts at 30 Hz. The users of these different techniques all claim they could perform cavity preparations without giving injection anesthesia and the patients are comfortable.

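### Sections 4.1 and 7.1 place small lesions under two ablation settings, 4.5 W and 2 W, and no visible text says which applies

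*Protocol*

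**What the plan says.** The operating steps in Section 7.1 (Preparation of Lesion) have two headings. Heading A, for small preparations, reads "Waterlase MD settings: 4.5W, 15Hz, 65% air, 60% water". Heading B is titled "Laser ablation- Small and Medium Preparation" and reads "Waterlase MD settings: 2W, 15Hz, 65% air, 60% water". Section 4.1 has the same two settings with slightly different labels: small preparations at 4.5 W, 15 Hz, then "Small to medium preparations will be performed as follows", at 2 W, 15 Hz.

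The size classes are divided differently elsewhere:

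- Section 2.1 gives dimensions for small lesions and, separately, for medium and large lesions.
- The VAS explanation in Section 4.1 analyses hand raises separately for small and for medium/large preparations.
- Table 1 admits small and medium cavities.

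On the pair, Sections 3, 5.1.4 and 7.1 describe both teeth as cut at the higher power, one after LLLT and one without it. Sections 3 and 5.1.4 and Table 1 require the two cavities to be of the same type and similar size. The only instruction about keeping settings constant concerns one tooth after a pain halt: "For patients who refuse anesthetic, the procedure will be continued at the same settings".

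**The concern.** The setting is meant to follow from lesion size, but for small lesions size does not determine it. Two consequences follow from the text.

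First, the small group can contain patients cut at 4.5 W and patients cut at 2 W. A pain score or hand-raise result for that group would then not say at which power it was obtained. Section 2.1 explains that the study concentrates on specific parameters because users choose many different powers and frequencies, so an open choice of power works against that aim.

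Second, nothing stops the two teeth of a small pair from being cut at different powers. The within-patient pair is the comparison that tests LLLT. The steps have one tooth conditioned and cut, then the other cut without conditioning, so the operator knows which is which. An open choice of power made with that knowledge could mix the LLLT effect with a power effect.

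**Working it through.** The protocol states no figure for this point, so the check sets the texts side by side and adds a little arithmetic.

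**1. Is the overlap real?** Small appears under both settings in Section 4.1 and again in Section 7.1, with different wording (small to medium in one, small and medium in the other). An error in reading the PDF is therefore unlikely. The small lesion of Section 2.1 (1.5 x 1.5 x 2 mm) fits both headings.

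**2. How far apart are the settings?** Inputs are from Section 7.1.

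- Power ratio: 4.5 / 2 = 2.25.
- Pulse energy = power / frequency. Heading A: 4.5 / 15 = 0.300 J = 300 mJ. Heading B: 2 / 15 = 0.133 J = 133 mJ. The frequency is the same, so this ratio is also 2.25.

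Section 2.1 puts heading A's setting in its high-power group: "A few of these high power examples are 6 Watts at 20 Hz, 4.5 Watts at 15 Hz, or 3 Watts at 10 Hz". It calls 2 W, there at 30 Hz, relatively low. By pulse energy, which the protocol does not itself report:

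| Section 2.1 group | Settings (W/Hz) | Pulse energy (mJ) |
|---|---|---|
| High | 6/20, 4.5/15, 3/10 | 300, 300, 300 |
| Moderate | 4.5/20, 3.5/15, 2.5/10 | 225, 233, 250 |
| Relatively low | 2/30 | 67 |

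Heading A (300 mJ) matches the high group. Heading B (133 mJ) lies below the moderate group.

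**3. Does the higher-power wording choose between them?** The contrast is with the LLLT setting of 0.25 W. 2 / 0.25 = 8 and 4.5 / 0.25 = 18, so both settings are higher than LLLT and the wording fits either.

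**4. What can happen to a small pair?** The text permits four combinations.

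| LLLT tooth | Other tooth | Power difference | Bias in the LLLT contrast |
|---|---|---|---|
| 4.5 W | 4.5 W | 0 | 0 |
| 2 W | 2 W | 0 | 0 |
| 4.5 W | 2 W | +2.5 W | d |
| 2 W | 4.5 W | -2.5 W | -d |

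Here d is the mean VAS difference between cutting at 4.5 W and at 2 W, taken as adding to the LLLT effect. The mean bias over small pairs is d x (share of row 3 minus share of row 4). The protocol gives neither d nor the shares, so no VAS figure can be attached. With rows 3 and 4 empty, the bias is 0.

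**5. What remains if every pair is cut at one power?** Rows 1 and 2 can still both occur across patients. The LLLT contrast within each pair is then unbiased from this source, but the small group pools two powers.

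**The case against.** The strongest reply is that the protocol clearly intends like-for-like cutting. It defines the two procedures by LLLT alone, describes both cuts as made at the higher power, assigns settings by size and matches pairs on size. A matched pair meets the same heading, or the same ambiguity, on both teeth. Only an operator who treated like lesions differently would produce a discordant pair, and no text suggests that. This stands, and it limits the point: a reader might infer that the LLLT comparison is confounded by power, but the protocol does not support that. It shows a missing rule, not a plan to treat the two teeth differently.

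A reader might also infer that leaving the cutting to the operator's preferred technique is a further defect. It is not one on this text. Power, frequency, air and water are fixed under each heading, Section 2.1 gives dimensions per size class, and the remaining hand technique is ordinary clinical discretion. Nor does anything show that different operators would treat the two teeth, since the work is done in one office (Section 6.3).

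It can be said that heading B obviously means medium, or medium and large. That is probably right, but two sections say otherwise, and if it is a slip the correction is a rename.

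It can also be said that pooling two powers does not bias a within-patient contrast and that the objectives do not ask for a comparison of settings. Both are true. Pooling only blurs which setting a small-group result describes.

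Finally, a figure at the start of Section 4.1 is not available, so the statement that nothing chooses between the settings covers the visible text only.

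**Conclusion.** The point holds as a contradiction in an operative treatment setting: small lesions are assigned both 4.5 W and 2 W at 15 Hz, a 2.25-fold difference. As written, the small group may mix the two powers, and a small pair could be cut at both without a protocol breach. The effect on VAS is unknown in size and direction. On the most likely practice, one setting per pair, the bias in the LLLT comparison is zero, and what remains is uncertainty about which power the small-group results describe. The conclusion rests on the visible text and on the operator knowing which tooth had LLLT, which follows from the order of the steps. It is a minor point, worth acting on because the correction costs almost nothing.

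**What to change.** In Sections 4.1 and 7.1:

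1. Give each size class one setting. If it is the intent, rename heading B to medium (and large, if large lesions are enrolled). Otherwise state which small lesions are cut at 2 W. Use the same size labels in Section 2.1, Table 1 and the hand-raise analysis.
2. Add: *Both teeth of a patient are cut at the same laser setting, fixed and recorded before the LLLT tooth is drawn.*

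The cost is a few words in two sections and one recorded entry per patient, which the case report form may already hold. The downside is that the operator cannot change the setting between the two teeth without a recorded deviation. Fixing the setting before the draw keeps knowledge of the arm from influencing it. It does not blind the operator while cutting.
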